21.1 Statistical and Analytical Plans (SAP)

A formal SAP will be developed prior to database lock and unblinding.

21.2 Statistical Hypotheses

Hypothesis 1a: Within-group circulating CBD levels will stabilize within one week, i.e. pre-CBD dosing (12 hour) levels obtained after 1 week of treatment will not differ from those obtained after 4 weeks of treatment at each dose.

Hypothesis 1b: Circulating CBD levels obtained at the 1200 mg/day dose will be comparable to those associated with anti-additive effects in animal models, i.e., in the range of 200-400 ng/ml.

Hypothesis 1c: No clinically significant cognitive or motoric impairments, CBD-related serious adverse events, or persisting adverse effects will be observed.

Hypothesis 2a: Relative to placebo, CBD will improve self-report measures of craving, anxiety, mood, and self-efficacy.

Hypothesis 2b: Relative to placebo, CBD will be associated with decreased stress- and alcohol cue-induced craving and physiological stress response

Hypothesis E: Relative to the placebo-treated group, CBD-treated participants will have fewer heavy drinking days during and for four weeks after treatment with 1200mg/day CBD vs. placebo.

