3.2.1 Preclinical Data

In rodent models, CBD reduces cue-induced heroin seeking, potentiates extinction of cocaine- and amphetamine-induced conditioned place preference [73], and normalizes heroin-seeking-induced changes in glutamatergic GluR1-containing amino-hydroxy-methyl-isoxazolepropionic (AMPA) receptors and CB1 receptor expression in the nucleus accumbens [74]. Work done in the laboratory of [name] (consultant on the current proposal) demonstrated that transdermal CBD at a dose yielding serum CBD concentrations of 300-400ng/ml reduces stress- and cue-induced alcohol- and cocaine- seeking in rodents, with effects lasting up to 138 days post-CBD treatment for alcohol [75]. This regimen also reduced anxiety-like behavior in alcohol-exposed, cocaine-exposed, and drug-naïve rodents without impacting locomotor activity or cue- or stress- induced reinstatement for a sweet solution, and reversed impulsive-like behavior induced by alcohol intoxication in a delay discounting task 6-15 days after the cessation of treatment. Another recent report also demonstrated CBD's ability to reduce the reinforcing effects of alcohol at an identical dose of CBD delivered subcutaneously in a microparticle formulation also designed to provide continuous controlled release of CBD [76].

Studies of CBD's effects on addiction-related behaviors in human participants are limited. The only study to assess the impact of CBD on alcohol-related behaviors found no impact of 200mg of CBD on symptoms of intoxication in healthy volunteers [77]. However, high concentrations of CBD in cannabis are related to lower attentional bias toward drug stimuli and lower self-rated liking of cannabis-related stimuli relative to cannabis with a low ratio of CBD to THC [78], CBD may reduce cigarette smoking in dependent humans [79], and a single case study reported that daily CBD prevented marijuana withdrawal symptoms [80].

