3.2.3 Dose Rationale (if applicable)

CBD has been given up to 600 mg daily orally for cannabis dependence [80], and the one existing human study of CBD's impact on the acute effects of alcohol used a dose of 200 mg [88]. CBD was given to patients with schizophrenia up to 1280 mg/day [89], and Phase 3 trials of CBD for seizure disorders used doses of 20 mg/kg/day oral CBD solution (1400 mg/day for a 70 kg person) [9, 11].

Consistent and clinically significant effects on fear and anxiety in the absence of intoxicating, psychotomimetic, and psychotropic effects have been observed with oral dosing in the range of 300-600 mg/day [90]. However, preliminary work performed by [name] and others [76] indicates that higher doses (>30mg/kg/day transdermal/subcutaneous) yielding serum CBD concentrations in the range of 300-400ng/ml are required to reduce alcohol-reinforced reward-seeking behaviors in rodents.

Oral dosing of CBD is complicated by limited oral absorption, which is similar to THC at approximately 6% [91], and by the possibility that high doses of CBD could convert to THC when delivered orally [92, 93]. However, oral delivery of CBD in a sesame-oil formulation at a dose of 12mg/kg (roughly equivalent to 1000mg/day adjusted for average human body weight) was shown to yield serum concentrations within the targeted range in rats [94]. We therefore will administer CBD vs. Placebo orally in a lipid-based formulation at 600mg/day for an initial period of 4 weeks, followed by 1200mg/day for an additional 4 weeks, to reach our target circulating levels of 300-400ng/ml in a human AUD sample. Two studies in humans have shown no progressive accumulation of CBD levels with repeated daily dosing, including following 6 weeks of oral administration of 700mg/day CBD [95, 96], and preliminary data with transdermal CBD up to 30mg/kg/day in rodents shows no serum accumulation over 7 days of treatment ([name], unpublished data). Therefore, under the proposed dosing regimen we expect to achieve steady-state circulating levels of CBD within a week.

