4.1 Primary Objective

The primary objective of this study is to assess circulating cannabinoid levels and safety of CBD administered to patients with AUD at doses calculated to yield circulating CBD levels comparable to those that produced clinically relevant effects in animal models of AUD. We predict that within-group circulating CBD levels will stabilize within one week (i.e. pre-CBD dosing levels obtained after 1 week of treatment will not differ from those obtained after 4 weeks of treatment at each dose), that circulating CBD levels obtained at the 1200 mg/day dose will be comparable to those associated with anti-addictive effects in animal models, (i.e., in the range of 200-400 ng/ml), and that no clinically significant cognitive or motoric impairments, CBD-related serious adverse events, or persisting adverse effects will be observed.

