21.3.2 Analysis of the Primary Endpoint(s)

For Hypothesis 1a, acute circulating levels of CBD will be assessed in CBD-treated participants 45 minutes after initial administration (T1, T4), and 45 minutes after administration of the morning dose of medication following 1 day (T2, T5), 1 week (T3, T6), and 4 weeks (T4, T7) of treatment with each dose of CBD. Additionally, circulating levels of CBD will be assessed in CBD-treated participants 12 hours after ingestion of the preceding evening dose following 1 week (T3, T6) and 4 weeks (T4, T7) of administration of each dose of CBD. Levels of CBD (mean and standard deviation) will be reported at each timepoint and effects of dose and timepoint will be evaluated. For Hypothesis 1b, circulating CBD levels (mean and standard deviation) 45 minutes after administration of the morning dose of medication following 1 week (T3, T6) and 4 weeks (T4, T7) of treatment with each dose of CBD will be reported in CBD-treated participants. For Hypothesis 1c, between-group differences on psychomotor tasks (T1-T8), cognitive measures (T3, T6) and number of adverse events (T1-T9) will be assessed.

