21.3.4 Safety Analyses

Means and standard deviations of acute circulating CBD and THC levels within CBD-treated participants 45 minutes after initial administration (T1, T4), and 45 minutes after administration of the morning dose of medication following 1 day (T2, T5), 1 week (T3, T6), and 4 weeks (T4, T7) of treatment with each dose of CBD will be assessed to determine whether target circulating levels of CBD have been achieved, and whether metabolic transformation of CBD to THC has occurred.

Means and standard deviations of change in 12 hour circulating CBD levels from 1 week to 4 weeks of treatment (T3 to T4, and T6 to T7) within CBD-treated participants will be presented to determine whether extended treatment with CBD results in accumulation of CBD.

The number of participants within each treatment group that were able to pass a battery of psychomotor field sobriety tasks (walk-and-turn task, one-leg stand, Romberg's test, finger-finger test, and counting backwards [97]) within 2 hours of the initial administration of each dose of CBD vs. placebo (T1 and T4) will be analyzed as summary statistics during treatment.

AEs and SAEs, when present, will be collected on an AE Case Report Form at study visits. The form will include an assessment of clinical significance and study relatedness. Serious Adverse Events (SAEs) will be documented on an additional SAE form. These CRFs will be based on those used in recent NIDA Clinical Trials Network trials. To further assess abuse potential, visual analog scales will be used to assess abuse potential. Scales will include desire to use the study medication again, desire to use the study medication again for pleasurable intoxication ("to get high"), and craving for the study medication.

The study may be stopped if there are untoward and concerning levels of Adverse Event (AE) or Serious Adverse Event (SAE) outcomes attributable to CBD or study participation. If the DSMB finds it is likely that CBD is contributing to negative outcomes, they will consider solutions including protocol changes or potentially stopping the study.

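### Hypothesis 1b uses a CBD range of 200-400 ng/ml where the protocol's own animal evidence and stated human target are 300-400 ng/ml; one range should be settled before unblinding

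*Combined protocol and SAP*

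**What the plan says.** **The range.** Section 4.1 predicts levels at 1200 mg/day "comparable to those associated with anti-addictive effects in animal models, (i.e., in the range of 200-400 ng/ml", and Section 21.2 repeats this as Hypothesis 1b, with levels "comparable to those associated with anti-additive effects in animal models, i.e., in the range of 200-400 ng/ml". Section 3.2.1 reports that "transdermal CBD at a dose yielding serum CBD concentrations of 300-400ng/ml reduces stress- and cue-induced alcohol- and cocaine- seeking in rodents". Section 3.2.3 says that higher doses "yielding serum CBD concentrations in the range of 300-400ng/ml are required to reduce alcohol-reinforced reward-seeking behaviors in rodents", and that the trial doses were chosen "to reach our target circulating levels of 300-400ng/ml in a human AUD sample".

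**The analysis of 1b.** Section 21.3.2 plans a description only: "For Hypothesis 1b, circulating CBD levels (mean and standard deviation) 45 minutes after administration of the morning dose of medication" at 1 and 4 weeks of each dose. It gives no interval and no rule for calling a result in range. Section 21.3.4 says that 45-minute levels "will be assessed to determine whether target circulating levels of CBD have been achieved", without giving the target as a number.

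**The no-difference predictions.** Hypothesis 1a states that 12-hour "levels obtained after 1 week of treatment will not differ from those obtained after 4 weeks of treatment" at each dose. Hypothesis 1c predicts no clinically significant impairment, no CBD-related SAEs and no persisting adverse effects. Section 21.3.8 says that a null difference between groups is hypothesised for the primary safety outcomes. Sections 21.3.1, 21.3.2 and 21.3.4 plan mixed models, group comparisons, pass counts, and means with standard deviations. No confidence interval is mentioned. Section 21.1 leaves the formal SAP to be written before lock and unblinding.

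**The concern.** A primary hypothesis carries a numerical range that differs from the evidence it claims to summarise. If the mean level at 1200 mg/day falls between 200 and 300 ng/ml, one reader can report that 1b was met and another that the target was missed, each citing current protocol text. Left open until the levels are known, the choice of range could follow the result.

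A lesser matter concerns 1a and 1c. Both predict the absence of something in a small sample. A p-value does not tell the reader how large a change or event rate is still compatible with the data, and the plan does not say how a null finding will be worded.

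**Working it through.** **1. The sections side by side**

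| Section | Role of the range | ng/ml |
|---|---|---|
| 3.2.1 | Rodent effect on alcohol and cocaine seeking | 300-400 |
| 3.2.3 | Level required in rodents | 300-400 |
| 3.2.3 | Target in the human sample | 300-400 |
| 4.1 | Animal-effect level predicted at 1200 mg/day | 200-400 |
| 21.2 (1b) | Same as 4.1 | 200-400 |
| 21.3.4 | Target to be checked | none given |

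The upper limits agree. The zone in dispute is 300 - 200 = 100 ng/ml out of 400 - 200 = 200 ng/ml, or half of 1b's range.

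**2. Precision of the 1b estimate**

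Forty participants randomised 1:1 (Section 5.1) gives about 20 on CBD. The documents give no between-person variability, so I assume a coefficient of variation (CV) of 50, 75 or 100% and log-normal levels. Then sigma = sqrt(ln(1 + CV²)), and the 95% limits are the geometric mean divided and multiplied by exp(t × sigma / sqrt(20)), with t(0.975, 19) = 2.093. For an observed geometric mean of 250 ng/ml, chosen to sit in the disputed zone:

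| Assumed CV | sigma | Factor | 95% CI (ng/ml) |
|---|---|---|---|
| 50% | 0.472 | 1.247 | 200-312 |
| 75% | 0.668 | 1.367 | 183-342 |
| 100% | 0.833 | 1.476 | 169-369 |

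Each of these intervals includes 300, so an estimate in this zone may not settle which side of 300 the true mean lies on. The interval should accompany the estimate.

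**3. Precision for 1a**

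Section 21.3.4 already plans the mean and SD of the within-person change in 12-hour levels (T3 to T4, T6 to T7). The 95% CI half-width is t × SD / sqrt(n):

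- n = 20: 2.093 / 4.472 = 0.47 SD of the change.
- n = 15 (assumed losses): 2.145 / 3.873 = 0.55 SD of the change.

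On the ratio scale, I assume a within-person CV of 30, 50 or 70%. The SD of the log difference is sqrt(2 ln(1 + CV²)). With n = 20, an observed week 4/week 1 ratio of 1.00 has 95% limits of about 0.82-1.21, 0.73-1.37 and 0.66-1.52 respectively.

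**4. Precision for 1c**

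- Zero events in n participants: the exact two-sided 95% upper limit is 1 - 0.025^(1/n). For n = 20 this is 16.8%; for n = 15 it is 21.8%. By the same formula, 20 of 20 passing the sobriety tests leaves a failure rate of up to 16.8% not excluded.
- Between-group score at one visit, 20 per arm: half-width t(0.975, 38) × sqrt(2/20) = 2.024 × 0.316 = 0.64 SD. A repeated-measures model may do better.

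**5. The plan's own power figure**

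Section 21.4 gives a detectable effect of about d = 0.2 for 1a and 1c at power 0.95, alpha 0.05, with 40 participants in 2 groups. It does not give the number of measurements or their correlation, so the figure cannot be reproduced from the document. A value near 0.2 does arise as Cohen's f for a group-by-time interaction. With N = 40, 6 time points and an assumed correlation of 0.5, the noncentrality is f² × N × m / (1 - rho) = 0.206² × 40 × 6 / 0.5 = 20.4 on 5 and 190 degrees of freedom, which gives power 0.95. That design does not match 1a, which uses only the CBD arm. No conclusion about power is drawn here.

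**The case against.** **On 1b.** The word comparable is loose, and 200-400 may be meant as a tolerance around 300-400. The source for 200 may also lie in cited animal work. Moreover, 1b has no test or decision rule: the same mean and SD would be published under either range, and readers could compare them with both. Most of this stands. It limits the effect to how a result of 200-299 ng/ml is described, and nothing in the document suggests that such a result is likely. But the text does not call 200 a tolerance, and the target check in Section 21.3.4 remains undefined.

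**On 1a and 1c.** A reader might infer that the plan will treat a non-significant result as proof of stability or safety. The document does not say so. For 1a, the planned mean and SD of the change yield a confidence interval once n is known, so the gap is one of presentation. The SAE part of 1c is a prediction about this sample and can be checked by counting. The between-group part, which rests on Section 21.3.8, is where an interval adds most. These objections are why the point on 1a and 1c is an improvement and not an error.

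**On power.** A reader might also infer from d = 0.2 that the power claim is false. With the repeated-measures assumptions unstated, the document supports only the narrower statement that the figure cannot be verified.

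**Conclusion.** The range conflict is real and lies in current text. Sections 4.1 and 21.2 disagree with Sections 3.2.1 and 3.2.3 on the lower limit, and Section 21.3.4 depends on a target it does not number. The effect is confined to results from 200 to just under 300 ng/ml. This is worth fixing because the hypothesis is primary and the choice should be made before the levels are known. It does not follow that 200 is wrong or that 300 is right; the document does not settle that.

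Intervals and bounded wording for 1a and 1c are a secondary improvement. The 16.8% limit assumes 20 participants on CBD and no events. The other widths rest on assumed CVs or numbers of completers, or are given in SD units, because the document states no variability or dropout rate. The range conflict depends on none of these assumptions.

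**What to change.** **Before unblinding, for 1b:** reconcile Sections 3.2.1, 3.2.3, 4.1, 21.2 and 21.3.4 to one sourced range. Alternatively, state that 200-400 is a tolerance around 300-400, or report 1b against both ranges. Give the T6 and T7 45-minute levels with 95% CIs.

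**In the same SAP edit, as an improvement:**

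- 1a: report the week 4 versus week 1 change in 12-hour CBD at each dose with a 95% CI, from the change data already planned.
- 1c: report between-group differences with 95% CIs, and exact CIs for AE, SAE and sobriety-pass proportions.
- Word the conclusions as the largest change or rate not excluded.
- Include all treated participants in the AE and SAE denominators. Section 7.1.9 limits the primary analyses to participants who complete through T7, so this is a change of analysis set and should be declared as one.
- Do not cite the d = 0.2 of Section 21.4 in support of a null result unless its repeated-measures assumptions, and whether it is a d or an f, are stated.

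**Cost:** SAP wording, a declared change to the safety denominators, and intervals from data already collected. No new visits or samples are needed. The downside is that 1a and 1c will probably be reported with wide intervals rather than as confirmed.

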21.3 Description of Statistical Methods

21.3.1 General Approach

The distributional characteristics of the measures used to investigate the aims of the study will be assessed and data transformations will be explored if necessary. For all hypotheses, linear mixed effects models will be constructed including treatment group as a fixed between-subjects factor, time (T0-T9) as a fixed within-subjects factor, and subject as a random effect. Treatment groups will also be compared on baseline measures of alcohol consumption (% drinking days and % heavy drinking days), alcohol craving (PACS), anxiety (BAI), mood (BDI-II), and self-efficacy (AASE), and baseline scores on these measures will be utilized as covariates for hypothesis evaluation.

21.3.2 Analysis of the Primary Endpoint(s)

For Hypothesis 1a, acute circulating levels of CBD will be assessed in CBD-treated participants 45 minutes after initial administration (T1, T4), and 45 minutes after administration of the morning dose of medication following 1 day (T2, T5), 1 week (T3, T6), and 4 weeks (T4, T7) of treatment with each dose of CBD. Additionally, circulating levels of CBD will be assessed in CBD-treated participants 12 hours after ingestion of the preceding evening dose following 1 week (T3, T6) and 4 weeks (T4, T7) of administration of each dose of CBD. Levels of CBD (mean and standard deviation) will be reported at each timepoint and effects of dose and timepoint will be evaluated. For Hypothesis 1b, circulating CBD levels (mean and standard deviation) 45 minutes after administration of the morning dose of medication following 1 week (T3, T6) and 4 weeks (T4, T7) of treatment with each dose of CBD will be reported in CBD-treated participants. For Hypothesis 1c, between-group differences on psychomotor tasks (T1-T8), cognitive measures (T3, T6) and number of adverse events (T1-T9) will be assessed.

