7.1.5 Dosing and Administration

Participants will self-administer CBD vs Placebo twice daily for a total of 600mg/day CBD vs. Placebo for the first four weeks of treatment and 1200mg/day CBD vs. Placebo for weeks 5-8 of treatment. For the first four weeks of treatment, participants will self-administer two 200mg capsules every morning following a light meal at approximately the same time of day, and an additional single 200mg capsule approximately 12 hours later following a light meal. During weeks 5-8 of treatment, participants will self-administer three 200mg capsules every morning following a light meal at approximately the same time of day, and an additional three 200mg capsules approximately 12 hours later following a light meal.

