7.3.2 Assessment of Subject Compliance with Study Intervention

To maximize medication compliance, we will implement a smartphone-assisted medication adherence platform [119] in which the subject takes a video of drug administration at each dose, and transmits this to study personnel. This program has been used successfully in previous studies and includes security provisions that ensure protection of confidentiality and privacy.

CONFIDENTIAL

This material is the property of the NYU School of Medicine and Langone Health
Do not disclose or use except as authorized in writing by the study sponsor

[name] CBD for AUD											
DOSE		600mg			1200mg			PHONE			
TIMEPOINT VARIABLE		T0	T1	T2	T3	T4	T5	T6	T7	T8	T9
		Screen	Baseline	1 day	1 wk	4 wks	4wk+1d	5 wks	8 wks	9 wks	12 wks
Inclusion / Exclusion Criteria		✓									
Informed Consent Quiz		✓									
Informed Consent Documentation		✓									
Confidential Contact Information		✓									
Demographics		✓									
Medical History		✓									
Family History		✓									
Physical Examination		✓									
Phenx Quality of Life "P"		✓									
Phenx Sub Alc Cig		✓									
CIVVA-Ar		✓									
CAPS											
SCID-5 Results		✓									
Screen Menstrual Calendar		✓									
Urine Pregnancy Test		✓	✓								
Urine Drug Screen		✓									
Screening Timeline Followback		✓									
Serum Pregnancy Test Results		✓									
Screening Blood/Urinalysis Lab Results		✓									
Concurrent Medications		✓	✓	✓	✓	✓	✓	✓	✓	✓	
Inclusion Exclusion Criteria Checklist		✓									
Screen Visit Form		✓									
CBD/THC/AEA Serum Levels											
Cannabinoid Blood Collection [Trough]		✓									
Cannabinoid Blood Results [Trough]		✓									
Cannabinoid Blood Collection [Peak]		✓	✓	✓	✓	✓	✓	✓	✓	✓	
Cannabinoid Blood Results [Peak]		✓	✓	✓	✓	✓	✓	✓	✓	✓	
CDT											
CDT Blood Collection		✓									
CDT Blood Results		✓									
LFT		✓									
LFT Blood Collection		✓									
LFT Blood Results		✓									
SAFETY & Psychomotor Effects											
Vital Signs		✓	✓	✓	✓	✓	✓	✓	✓	✓	
Adverse Events		✓	✓	✓	✓	✓	✓	✓	✓	✓	
Alcohol Breathalyzer		✓	✓	✓	✓	✓	✓	✓	✓	✓	
Addiction Research Center Inventory "P"		✓	✓	✓	✓	✓	✓	✓	✓	✓	
Field Sobriety Tests		✓	✓	✓	✓	✓	✓	✓	✓	✓	
Cognitive Function											
Rey Auditory Verbal Learning Task Results						✓					
Mental Rotation Task Results						✓					
Time Production Task						✓					
WM Span Tasks Results						✓					
AUD-Related Domains											
Readiness Rulers "P"		✓				✓					
Treatment Goal "P"		✓				✓					

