8.2.2 Specimen Shipment

Specimens will be shipped monthly on dry ice with appropriate labeling for shipment of biological specimens on dry ice, according to the study's SOP. A specimen tracking log will be utilized to record dates and times

CONFIDENTIAL

This material is the property of the NYU School of Medicine and Langone Health
Do not disclose or use except as authorized in writing by the study sponsor

that each specimen was collected and shipped. Specimens may be shipped overnight between 9:00am and 5:00pm on business days except Fridays.

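### The week 1 versus week 4 pre-dose CBD comparison for Hypothesis 1a uses nominal sampling times, although the preceding evening dose is taken at home at an approximate time

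*Combined protocol and SAP*

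**What the plan says.** Hypothesis 1a (21.2) concerns pre-dose levels after 1 week of treatment and predicts that they "will not differ from those obtained after 4 weeks of treatment at each dose". Section 21.3.2 defines the samples by a nominal interval: "circulating levels of CBD will be assessed in CBD-treated participants 12 hours after ingestion of the preceding evening dose", at T3, T4, T6 and T7. Section 21.3.4 uses the T3-to-T4 and T6-to-T7 change in the same nominal 12-hour level to judge whether CBD accumulates.

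The dosing text is looser. Under 7.1.5 participants take the evening dose themselves: "an additional single 200mg capsule approximately 12 hours later following a light meal" in weeks 1-4 and "an additional three 200mg capsules approximately 12 hours later following a light meal" in weeks 5-8. The pre-dose draw is made at the clinic visit (8.3.3), and no clock time for visits is stated.

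The general model (21.3.1) has "time (T0-T9) as a fixed within-subjects factor, and subject as a random effect". Levels are summarised by mean and standard deviation at each timepoint. No section gives a sampling window, a rule for off-time samples or a term for actual time since dose.

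Two records bear on timing. For adherence, "the subject takes a video of drug administration at each dose, and transmits this to study personnel" (7.3.2, repeated in 21.3.5). For samples, "A specimen tracking log will be utilized to record dates and times" of collection and shipment (8.2.2). Neither is linked to the analysis of CBD levels.

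**The concern.** A pre-dose level depends on how long ago the last dose was taken. Here that interval starts at home, at an approximate time, and ends when blood is drawn at the clinic. If it differs between the week 1 and week 4 visits, the measured level differs even when exposure is stable. The plan's model attributes all of that difference to visit.

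Hypothesis 1a is a primary hypothesis, tested within the CBD arm of about 20 people (40 randomised 1:1). It predicts no difference and states no equivalence margin. Random timing error widens the spread of the week 4 minus week 1 difference and so makes the predicted answer easier to reach. A shift in the average interval would move the difference itself and could be read as accumulation or decline.

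**Working it through.** **The plan's own figures.** The plan gives no half-life, within-person variability or expected spread of dose times, so no timing figure can be reproduced. The only number attached to Hypothesis 1a is the detectable effect of about d = 0.2 at 95% power in 21.4. It does not reproduce for a paired comparison of 20 CBD participants, where the detectable effect is d = 0.85 (two-sided alpha 0.05). That is a separate point, and nothing below depends on it.

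**Inputs.** From the documents: nominal interval 12 h (21.3.2); approximate evening dosing (7.1.5); 40/2 = 20 CBD participants; alpha 0.05 (21.4). Assumed: first-order decline; half-life 4, 8, 12 or 24 h; within-person coefficient of variation (CV) 30%; standard deviation (SD) of the dose-to-sample interval 1 or 2 h; a true week 1 to week 4 rise of 30% where power is computed.

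**Step 1: one sample taken late.** Fractional fall = 1 - 2^(-delay/half-life). For 2 h and a half-life of 8 h this is 1 - 2^(-0.25) = 0.159.

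| Delay | 4 h | 8 h | 12 h | 24 h |
|---|---|---|---|---|
| 1 h | 16% | 8% | 6% | 3% |
| 2 h | 29% | 16% | 11% | 6% |
| 3 h | 41% | 23% | 16% | 8% |

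**Step 2: random timing error.** With CV 30%, the SD of the difference in log level between two visits is sqrt(2 × ln(1 + 0.3²)) = 0.415. Timing error adds a component with SD sqrt(2) × SD(interval) × ln 2 / half-life. For SD 1 h and half-life 4 h this is 0.245, and the total is sqrt(0.415² + 0.245²) = 0.482, a rise of 16%.

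A true 30% rise is ln 1.3 = 0.262 on the log scale, or 0.262/0.415 = 0.63 SD. The paired two-sided t test with n = 20 has 76% power without timing error. With timing error:

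| Interval SD | 4 h | 8 h | 12 h | 24 h |
|---|---|---|---|---|
| 1 h | 64% | 73% | 75% | 76% |
| 2 h | 41% | 64% | 70% | 75% |

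**Step 3: a systematic shift.** Suppose levels are truly stable but the average interval differs by 1 h between week 1 and week 4. The log difference is then ln 2 / half-life, which at 4 h is 0.173, or 0.173/0.415 = 0.42 SD. The chance of a significant result in the direction of the shift, nominally 2.5%, becomes about 43%, 14%, 9% and 5% at half-lives of 4, 8, 12 and 24 h (CV 30%, no random timing error added).

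**Step 4: which samples are affected.** The home evening dose sets the interval only for the pre-dose samples at T3, T4, T6 and T7. The 45-minute samples follow the morning dose. The first dose at each level (T1 and T4) is given at the site (7.3.1), and T3, T4, T6 and T7 each have a pre-dose and a 45-minute post-dose draw at one visit (8.3.3), so that interval lies within the visit. At T2 and T5 only a 45-minute sample is listed and the place of dosing is not stated.

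**The case against.** The strongest case against is that this is ordinary detail for documents not available here. Section 8.2.1 refers blood draws to a study SOP, and 21.1 says that a formal SAP will follow before database lock. Both may well cover windows. Also, 7.1.5 does constrain the schedule, with a morning dose at roughly the same time each day and an evening dose about 12 hours later. This stands as a limit on the finding, but the present text specifies nothing, and the later SAP is the natural place for the change.

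A reader might infer four stronger things, and the documents do not support them.

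- **That all CBD samples are affected, including the 45-minute ones.** Step 4 shows otherwise. Only T2 and T5 leave a question, and it is about where the dose is taken.
- **That the plan treats off-time samples as exactly on time.** The 12-hour wording is a nominal label. No section says that deviations will be ignored.
- **That actual elapsed time is already known.** Collection times are logged. The dose video is described only as an adherence measure, and nothing says that its clock time is extracted or kept.
- **That Hypothesis 1a will be biased.** Error that averages to zero adds only variance. Bias needs a group-wide shift between the two visits. Visit content does differ (cognitive testing at T3 and T6, a 120-minute imagery task at T6, about two hours on site after the new dose at T4), so start times could differ, but no section says that they do. One participant whose visit moves by 2 h does not move the group mean by the figures in Step 1.

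It is also fair to say that 21.3.4 only presents means and SDs of change, without a test, and that the lack of an equivalence margin is a larger weakness of Hypothesis 1a than timing.

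**Conclusion.** The point holds for the pre-dose samples at T3, T4, T6 and T7, as a modest and correctable weakness in a primary analysis. The week 1 versus week 4 comparison and the accumulation summary rest on nominal times, with no window and no adjustment.

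Its size cannot be fixed from the documents. With a half-life of 12 h or more and deviations of about 1 h it is small: power for a 30% rise goes from 76% to 75% or is unchanged. With a 4 h half-life and a 2 h spread, power falls to 41%. The false-signal rates in Step 3 apply only if the average interval really shifts. All of these figures assume first-order decline, CV 30% and 20 evaluable CBD participants. Fewer completers would lower the power figures. This is an improvement worth making, not a defect that invalidates the analysis.

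**What to change.** In 21.3.2 and 21.3.4, or in the formal SAP before unblinding:

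1. Derive the actual time from the last evening dose to the pre-dose draw at T3, T4, T6 and T7, using the dose-video time and the specimen log. First confirm that the video time is captured. If it is not, record the participant's reported last-dose time at the visit. Flag any participant who missed the evening dose.
2. Log-transform CBD levels for the Hypothesis 1a mixed model and include elapsed time as a covariate. Under first-order decline, log level is linear in elapsed time, so a single linear term suits. Present the 21.3.4 change summary with the same adjustment beside the raw one.
3. Report the median and range of elapsed time at each of the four visits. This shows directly whether the interval shifted between T3 and T4 or between T6 and T7.
4. Add a sensitivity analysis restricted to samples within a prespecified window around 12 h. The documents give no basis for its width, so the team should set it and state the reason before unblinding.
5. State where the T2 and T5 doses are taken.

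The cost is one model degree of freedom, a small data merge, possibly one extra question at four visits, and fewer samples in the sensitivity analysis. The main analysis keeps every sample.
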